#### 4) All Interventions After First Use

As defined for the exploratory endpoint of all interventions post creation with duration of evaluation adjusted to start from first successful HD AV access use.

The first successful HD AV access use will be identified if:

On the EndoAVF Dialysis page:

• Date endoAVF Successfully Used with 2 Needles for Hemodialysis is not NULL.

The number of all Interventions after first successful HD AV access use per PY will be estimated by Poisson regression model with only the intercept term, and the estimate and 95% CI will be provided using the Wald method.

For all the endpoints described above, total number of interventions and number of interventions at each time point will be summarized.

#### 5.3.7 Primary Patency

The time interval for primary patency is defined as the time from HD AV access creation to the first one of the following events: access thrombosis; any facilitation or maintenance intervention intended to support maturation or cannulation, as well as those to maintain, or re-establish functionality; access abandonment.

The failure for primary patency will be identified for the first occurrence of one of the followings:

- Access thrombosis: on the Post-Procedure Intervention page, Type is checked as "Thrombosis"; or on the
  Core Lab Analysis Duplex Ultrasound: EndoAVF Arm page, and Type is checked as "Thrombosis";
  Note: if the result from the Core Lab Analysis Duplex Ultrasound: EndoAVF Arm page is not available,
  use the corresponding information from the Duplex Ultrasound: EndoAVF Arm to determine Thrombosis.
- Intervention: on the Post-Procedure Intervention page, Date of Post Procedure Intervention is not NULL, and Type of Intervention is checked as "Facilitation Support AVF Cannulation", and/or "Facilitation Support AVF Maturation" and/or "Maintenance";
- Access Abandonment (Permanent Abandonment): on the EndoAVF Abandonment page, Date of
  Abandonment is not NULL, and the question of "All Possible Attempts Have Been Made to Improve the
  Condition of the Access" is checked as Yes, and the question of "Could Further Endovascular
  Interventions Salvage the Access" is checked as No, and the question of "Could Further Surgical
  Revisions Salvage the Access?" is checked as No, and Reason for Abandonment is selected as "The
  Access is No Longer Viable" or "The Access is Viable but there are Complications that Require the
  Abandonment of the Access".

Kaplan-Meier (KM) analysis will be used to estimate the time interval of primary patency. The following definition will be applied:

- If any failure event(s) as described above occurs, the participant is considered as having the event (loss of primary patency), and the first failure event date will be used in the analysis.
- If the participant was as transferred to PD, or had a kidney transplant, or had access discontinuation, or discontinued before the end of a specific visit window (e.g., 180+30 = Day 210 for 6-month visit) without the event, the participant is considered as censored the earliest date among these events (i.e., PD start date, kidney transplant date, date of access discontinuation, last date of available study data including the unscheduled visit date).
- Otherwise, if the participant did not have any failure event and has passed a specific visit by the cutoff date of database lock, the participant will be censored at the end of the reporting time window (e.g., 180+30 = Day 210 for the 6-month reporting, 730+30 = 760 for the final 24-month reporting) for this analysis.

This endpoint will be evaluated on the AT population. The number of participants with events, number of participants censored, time to event (days), and proportion of participants with event free along with the 95% CI will be presented at 30-days, 6-weeks, 3-, 6-, 12-, 18-, and 24-months post creation using the KM method.

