1.2 Schema

1.3 Schedule of Activities

		dure		Participant Follow-Up (Section 6.4)						4.2)	
	Screening (Section 6.1)	Screening / Index Procedure (Section 6.2)	Post-Index Procedure / Discharge (Section 6.3)	30-Day (± 5 days)	6-Week (± 7 days)	3-Month (± 30 days)	6-Month (± 30 days)	12-Month (± 30 days)	18-Month (± 30 days)	24-Month (± 30 days)	Unscheduled (Section 6.4.2)
In-Clinic Visit	✓	✓	✓	√ †	✓		✓	✓			✓
Phone Call				†		✓			✓	✓	✓
Informed Consent	✓										
Eligibility	✓	✓									
Demographics / Medical History	✓										
Angiography (Procedural & Final)		✓									
DUS	✓	✓		✓	✓		✓ *	*			#
Clinical Exam	✓		✓	>	>		>	>			✓
Medication Assessment		✓									
QOL - EQ-5D Questionnaire	✓				✓		✓	✓		✓	#
QOL - SF-VAQ	✓				✓		✓	✓		✓	#
HD History and Status**	✓	✓		✓	✓	✓	✓	✓	✓	✓	✓
Intervention Assessment			✓	√ †	✓	✓	✓	✓	>	✓	✓
Adverse Event Assessment		✓	✓	√ †	✓	✓	✓	✓	✓	✓	✓
Deviations		✓	✓	√ †	✓	✓	✓	✓	✓	✓	✓

^{*} DUS required at these visits only if participant is not successfully dialyzing with the AVF created as part of this clinical investigation using 2-needle cannulation and / or if the participant's wrist artery was used for procedure access during the index procedure.

For participants into whom the WavelinQTM EndoAVF system was introduced but procedure success was not achieved, only the follow up at 30 days is required to collect adverse events and interventions. The visit for these participants may be completed by phone. Investigation participation for these participants ends after completion of this follow-up.

^{**}Determine and document if and how the participant has been and / or is receiving HD (AVF, CVC, etc.) and document the date of the participant's last HD session. Once HD (1- or 2-needle cannulation) is initiated via the AVF created as part of this investigation, HD details must be documented and detailed HD access data (e.g., cannulation logs) will be provided to the Sponsor or designee for review and analysis as per Section 6.4.1.

^{*} These items are required for those unscheduled visits that fall within an allotted investigation schedule follow-up window if the visit is used in place of an investigation scheduled follow-up for which these items are required.

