• All Interventions After First Use (Facilitation, Maintenance and HD Continuity Interventions)

As defined for the exploratory endpoint directly above with duration of evaluation adjusted to start from first successful HD AV access use.

• Primary Patency

The time from HD AV access creation to the first one of the following events: access thrombosis; any facilitation or maintenance intervention intended to support maturation or cannulation, as well as those to maintain, or re-establish functionality*; access abandonment (as defined in Section 4.4); the access reaches an access censoring event as specified a priori in this CIP; or analysis timepoint / clinical investigation end. *Excludes adjunctive and second stage procedures.

• Cumulative Patency

The time from HD AV access creation to access abandonment, when the access reaches an access censoring event as specified a priori in this CIP, or analysis timepoint / clinical investigation end.¹⁸

• Primary Functional Patency

The time from first successful HD AV access use for HD using 2-needle cannulation to the first one of the following events: access thrombosis; any facilitation or maintenance intervention intended to support maturation or cannulation as well as those to maintain or re-establish functionality*; access abandonment (as defined in Section 4.4); the access reaches an access censoring event as specified a priori in this CIP; or analysis timepoint / clinical investigation end. *Excludes second stage procedures.

• Cumulative Functional Patency

As defined for the secondary endpoint (see Section 4.2.2.2) evaluated through additional time intervals.

• CVC Exposure / Use

Data will be collected regarding CVC exposure and use.

- For participants with a CVC in place at the index procedure, data will be collected after HD AV access creation to investigate the duration of CVC use.
- For all participants, data will be collected to determine frequency of CVC placements, time to CVC removal, total days of CVC exposure, and total days of CVC use.

• DUS Juxta/Peri-Anastomotic Area and Perforator Vein Patency

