6.4 Participant Follow-Up

6.4.1 Follow-Up Intervals and Methods

All participants are to be followed according to the investigational site's SOC practices. In addition to the SOC visits, treated participants will have an investigation follow-up visit at 30-days and 6-weeks as well as 6- and 12-months post index procedure and will have a phone call follow-up at 3-, 18- and 24-months. For participants into whom the WavelinQTM EndoAVF System was introduced during the index procedure but procedure success was not achieved, only the follow up at 30-days will be completed and limited to the collection of safety events and interventions. This follow-up may be conducted by phone for these participants and investigation participation for these participants will end upon completion of this follow-up.

All follow-up must be performed by authorized delegated clinical investigation site team members. Follow-up windows will be calculated from the index procedure date. Refer to Section 1.3 for an overview of follow-up window time frames and requirements for each visit. The following data will be collected and documented on the appropriate eCRF for each follow-up unless otherwise specified for treated participants:

- DUS: A DUS assessment per the Ultrasound Guidelines must be performed at the follow-up visits at 30-days and 6-weeks for all treated participants and again at 6-and 12-months for participants not yet successfully dialyzing with the AVF created as part of this clinical investigation using 2-needle cannulation. The 6- and 12-month DUS are also required for participants that are using the AVF created as part of this clinical investigation but for whom procedure access was obtained at the wrist artery during the index procedure. The DUS for these participants will be limited to the examinations of the artery that was accessed during the index procedure. At minimum, images including the following characteristics are required and must be submitted to the Sponsor / Core Lab as per the details specified in the investigational site's regulatory binder:
 - o Arteries and veins of the AVF: Patency (including characterization of each stenosis, if present), and inner diameters. Brachial artery volume flow.
 - AV-anastomosis & juxta-anastomotic area: Patency (including characterization of each stenosis, if present).
 - o Cannulation veins: Patency (including characterization of each stenosis, if present) and inner diameters.

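### Primary patency takes access thrombosis only from the intervention and ultrasound pages, so a thrombosis recorded only as an adverse event is censored or dropped instead of counted as a failure

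*SAP*

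**What the plan says.** **Definition.** Protocol 4.3 defines primary patency as "The time from HD AV access creation to the first one of the following events: access thrombosis", then lists facilitation or maintenance interventions and abandonment as further events. Thrombosis stands alone in that list and need not be treated to count.

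**How SAP 5.3.7 finds a failure.**
- Thrombosis: "Access thrombosis: on the Post-Procedure Intervention page, Type is checked as" thrombosis, or the same finding on the core laboratory DUS page. If the core laboratory result is missing, the SAP says to "use the corresponding information from the Duplex Ultrasound: EndoAVF Arm to determine Thrombosis".
- Any facilitation or maintenance intervention.
- "Access Abandonment (Permanent Abandonment): on the EndoAVF Abandonment page", but only if a date is present, all attempts to improve the access are marked as made, both salvage questions are answered No, and one of two listed reasons is chosen.

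**Dating and censoring.** For failures, "the first failure event date will be used in the analysis". Without a failure, the participant is censored at the earliest of several dates, among them "date of access discontinuation, last date of available study data including the unscheduled visit date", or otherwise at the end of the reporting window.

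**When DUS is done.** All treated participants are scanned at 30 days and 6 weeks. For 6 and 12 months the schedule says "DUS required at these visits only if participant is not successfully dialyzing with the AVF created as part of this clinical investigation", or if the wrist artery was used for procedure access. For wrist-access participants who are using the fistula, Protocol 6.4.1 adds: "The DUS for these participants will be limited to the examinations of the artery that was accessed during the index procedure". The 3-, 18- and 24-month contacts are phone calls without DUS.

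**AEs.** The schedule of activities has AE assessment at every follow-up, including the phone calls. Protocol 8.4 requires the date of each AE to be recorded.

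**The concern.** The SAP's derivation is narrower than the protocol's definition. A thrombosis found clinically and left untreated may exist in the database only as an AE, a source that 5.3.7 does not consult. If use of the fistula stops but not every abandonment item is met, SAP 2.7 calls the case an access discontinuation. The failure then becomes the reason for censoring, which is informative.

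Section 5.3.9 takes its failures from 5.3.7 and uses a proportion. There, a participant with access discontinuation before the end of the window and no recorded failure is not evaluable and leaves the denominator.

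Both effects raise the reported patency. Primary patency is to be shown at 18 and 24 months, where no DUS is scheduled.

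**Working it through.** **1. The plan's own windows.** SAP 5.3.7 censors event-free participants at 180 + 30 = Day 210 (6-month reporting) and 730 + 30 = Day 760 (final reporting). Both reproduce.

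**2. Gaps between scheduled DUS visits** (from the schedule of activities: 30 ± 5 days, 42 ± 7 days, 180 ± 30 days, 365 ± 30 days).

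| Interval | Nominal gap (days) | Longest gap within windows (days) |
|---|---|---|
| Index to 30 days | 30 | 35 |
| 30 days to 6 weeks | 42 − 30 = 12 | 49 − 25 = 24 |
| 6 weeks to 6 months | 180 − 42 = 138 | 210 − 35 = 175 |
| 6 to 12 months | 365 − 180 = 185 | 395 − 150 = 245 |
| 12 months to Day 760 | no DUS | 760 − 395 = 365 to 760 − 335 = 425 |

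The last stretch is 365/760 = 48% to 425/760 = 56% of the 24-month window.

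**3. Where an untreated index-access thrombosis ends up.**

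| What is recorded | 5.3.7 | 5.3.9 (after first 2-needle use) |
|---|---|---|
| Thrombosis ticked on the intervention page | Failure | Failure |
| DUS finding | Failure | Failure |
| Abandonment, all items met | Failure at abandonment date | Failure |
| AE and access discontinuation only | Censored at discontinuation | Not evaluable if before window end |
| AE only | Censored at Day 760 or last data | No event if followed past the window |

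The last two rows contradict Protocol 4.3. The abandonment row is hard to reach without treatment: Protocol 4.4 says an access is not abandoned if all reasonable efforts have not been attempted and documented.

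**4. Dating.** The SAP does not say whether a DUS finding is dated at the scan. If it is, an untreated thrombosis between week 6 and month 12 could be dated up to 138–185 days late at nominal visits, or 175–245 days at the window extremes. Before the 6-week scan the delay is at most 35 days.

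**5. Effect of one missed late event (illustration).** Attrition is assumed to be 40% at 12 months and 60% at 24 months (Protocol 7.3).
- Followed at 12 months: 150 × 0.60 = 90. Followed at 24 months: 150 × 0.40 = 60.
- The Kaplan-Meier step for one event is S/n, with S the patency just before it and n the number at risk. If attrition is independent of patency, n = N × S with N the number followed, so the step is 1/N.
- 1/90 = 1.1 points; 1/60 = 1.7 points.

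This is the rise at the time of the event. It persists to 24 months if the participant is carried to Day 760. If the participant is censored at time t, it shrinks by the ratio of 24-month patency to patency at t, so 1.1 to 1.7 is then an upper figure.

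**The case against.** The case against has four parts.

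- **Other routes catch many cases.** Permanent abandonment is a failure. A participant who loses the fistula may need a catheter or a new access, and those procedures also go on the Intervention eCRF, where thrombosis might be ticked. SAP 5.3.7 uses Type separately from Type of Intervention, which suggests a finding field, but the form is not shown. Someone whose fistula has clotted is no longer dialysing through it, so the 6- and 12-month DUS would normally apply. This stands as a limit on frequency. It does not close the gap for a participant who already has a catheter, for an incident participant not yet on dialysis, or after 12 months.
- **Derivations may be completed in Appendix 2.** Its content is not available. This matters for the dating rule. It matters less for the thrombosis sources, which 5.3.7 states in full.
- **AE terms are less specific.** The access circuit in Protocol 8.3 runs from heart to heart, and the SAP has the events committee adjudicate seriousness and relatedness, not location. This is fair, and it is met by restricting the trigger to the index fistula or its outflow.
- **The endpoints are exploratory.** Under Protocol 7.6 they may not be reported at all. This stands and limits the importance of the point.

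A reader might infer that every untreated thrombosis after month 12 is carried as patent to Day 760, or that earlier thromboses are generally dated months late. The documents do not support either. Abandonment counts as failure, access discontinuation censors on its own date, treated events enter through the intervention page, and long delays are possible only for untreated, DUS-detected events between week 6 and month 12.

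**Conclusion.** The mismatch holds in limited form. SAP 5.3.7 omits a source needed to apply the protocol's own definition, and the resulting error favours the device. It affects only index-access thromboses with no thrombosis entry on the intervention page, no counted intervention, no DUS finding and no complete abandonment entry, mostly after the 12-month visit.

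The size per event is about 1.1 to 1.7 points, given 60 to 90 participants followed and attrition independent of patency. The documents give no number of such events. Multiplying by an assumed count to claim a bias of several points would have no basis in them. Late dating is an inference that depends on an unstated rule.

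Primary patency and primary functional patency are exploratory, and neither co-primary endpoint uses this derivation. The correction is worth making because it is cheap and restores the protocol definition.

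**What to change.** Amend SAP 5.3.7, and through it 5.3.9, before database lock:

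1. Add to the thrombosis trigger: *or a reported AE of thrombosis of the index AVF or its outflow, event date = AE start date*, using events-committee-adjudicated data where available.
2. Take the earliest date across the AE, intervention, DUS and abandonment pages.
3. State whether a thrombosis seen on DUS is dated at the scan or at a documented onset.
4. Limit the DUS trigger to the index access. Exclude the wrist artery used for procedure access, which Protocol 4.3 treats as a separate endpoint.

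No new visit or assessment is needed, since the AE data are already collected. The costs are some review of AE terms for location and a slightly lower reported patency. Settling this before lock avoids the appearance of a data-driven change.

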4.4 Applicable Endpoint Definitions

Access Abandonment (permanent abandonment) is defined as the point at which the access can no longer be used for one or two needle prescribed HD as it may be unable to provide adequate flows and / or is deemed unsafe for the participant, and the associated problem cannot be corrected by any further intervention, including medical, surgical, or endovascular interventions or rest.^{8,19} Participants with an abandoned index AVF will continue with follow-up through 24-months and data will be collected on safety and interventions.

A HD AV access is not considered abandoned:

- If the participant discontinues use of the AV access due to kidney transplant, initiation of PD, or participant preference.
- During the maturation period or while waiting for a second stage procedure unless the principal investigator (PI) determines the participant requires and they then receive an alternative HD vascular access.

- During planned interventions, including transposition.
- If all reasonable efforts have not been attempted (and documented) to improve the condition of the access for it to be used.

A discontinuation of use of the clinical investigation AVF for any reason that does not meet this definition of access abandonment will be considered a temporary interruption.

Access Circuit Censoring Events include participant transfer to PD, kidney transplantation or the event of a participants premature discontinuation in the investigation due to withdrawn consent, withdrawal by PI, Lost to Follow-Up (LTF), or participant death (refer to Section 6.5 for definitions).

Adjunctive Procedure(s): Procedure(s) completed during the index procedure (prior to leaving the procedure room) as part of Standard-of-Care (SOC) procedures. These may include procedures to facilitate maturation and / or cannulation of the AVF, procedures to maintain use of the AVF, procedures to ensure HD continuity, as well as procedures to address AFs.

Second Stage Procedure(s): Facilitation Interventions (as defined below) intended to support the cannulation of arterialized vein segments that are determined to be needed a priori to or at the time of the index procedure (i.e. pre-planned facilitation interventions intended to support cannulation). Second stage procedures will not count against the intervention or patency endpoints and will require completion of the Second Stage Procedures eCRF.

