#### **5.2.4** Cumulative Functional Patency

The time interval of cumulative functional patency is defined as the time from first successful HD AV access use for HD using 2-needle cannulation to access abandonment. This endpoint will be evaluated through 12-months. Additionally, for exploratory purposes, the endpoint will be evaluated through 6 months, 18 months, and 24 months.

Only the participants who have started 2-needle HD using the endoAVF will be considered as evaluable for this endpoint.

Access Abandonment (Permanent Abandonment) will be identified if:

On the EndoAVF Dialysis page, Date endoAVF Successfully Used with 2 Needles for Hemodialysis is not NULL and within a specific visit (e.g., within 395 days for 12 months).

and

On the EndoAVF Abandonment page, Date of Abandonment is not NULL and within a specific visit (e.g. within 395 days for 12 months), the question of "All Possible Attempts Have Been Made to Improve the Condition of the Access" is checked as Yes, and the question of "Could Further Endovascular Interventions

Salvage the Access" is checked as No, and the question of "Could Further Surgical Revisions Salvage the Access?" is checked as No, and Reason for Abandonment is selected as "The Access is No Longer Viable" or "The Access is Viable but there are Complications that Require the Abandonment of the Access".

The binary definition for cumulative functional patency is shown as below:

- If permanent abandonment, as detailed above, occurs on, or before, a specific visit (e.g., 365+30 = Day 395 for 12 months post creation), the participant is considered as having an event (loss of cumulative functional patency).
- If the participant was transferred to PD, or had a kidney transplant, or had access discontinuation, or discontinued before the beginning of a specific visit (e.g., 365-30 = Day 335 for 12 months post creation) without permanent abandonment, the participant is considered not evaluable and will not be included in the analysis.
- Otherwise, if the participant did not have permanent abandonment and has passed the specific visit window by the cutoff date of database lock, the participant is considered as not having an event.

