#### **5.3.8** Cumulative Patency

The time interval for cumulative patency is defined as the time from HD AV access creation to access abandonment.

Kaplan-Meier (KM) analysis will be used to estimate the time interval of cumulative patency. The following definition will be applied:

- If permanent abandonment (as detailed in Section 5.2.4) occurs, the participant is considered as having the event (loss of cumulative patency), and the corresponding abandonment date will be used in the analysis.
- If the participant was as transferred to PD, or had a kidney transplant, or had access discontinuation, or discontinued before the end of a specific visit window (e.g., Day 210 for 6-month visit) without the event, the participant is considered as censored at the earliest date among these events (i.e., PD start date, kidney

transplant date, date of access discontinuation, last date of available study data including the unscheduled visit date).

• Otherwise, if the participant is still in the investigation without the event and has passed a specific visit by the cutoff date of database lock, the participant will be censored at the end of the reporting time window (e.g., 180+30 = Day 210 for the 6-month reporting, 730+30 = 760 for the 24-month reporting) for this analysis.

This endpoint will be evaluated on the AT population. The number of participants with events, number of participants censored, time to event (days), and proportion of participants with event free along with the 95% CI will be presented at 6-, 12-, 18-, and 24-months post creation using the KM method.

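### The SAP patency rules put no date order on failures, so a failure after PD transfer or kidney transplant can count, against the plan's own first-of definition

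*SAP*

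**What the plan says.** **Definition.** Protocol 4.3 ends primary patency at the first of several events. After thrombosis, intervention and abandonment the list continues: "the access reaches an access censoring event as specified a priori in this CIP; or analysis timepoint / clinical investigation end". Protocol 4.4 says what these are: "Access Circuit Censoring Events include participant transfer to PD, kidney transplantation or the event of a participants premature discontinuation in the investigation". SAP 2.7.3.9 repeats the first-of definition. SAP 2.7.3.10, 2.7.3.11 and 2.7.2.4 likewise end cumulative, primary functional and cumulative functional patency at a censoring event.

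**Working rule for primary patency.** SAP 5.3.7 restates the interval without the censoring event and then gives three bullets in order:

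1. "If any failure event(s) as described above occurs, the participant is considered as having the event (loss of primary patency", dated at the first failure.
2. A participant who went to PD, had a transplant, had an access discontinuation or left before the end of the visit window, and who is without the event, is censored at the earliest of those dates.
3. Anyone else without a failure is censored at the end of the reporting window.

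**The other three.** SAP 5.3.8 has the same structure: "If permanent abandonment (as detailed in Section 5.2.4) occurs, the participant is considered as having the event (loss of cumulative patency". SAP 5.2.4 and 5.3.9 are binary proportions. In 5.2.4 the event bullet begins "If permanent abandonment, as detailed above, occurs on, or before, a specific visit", and PD or transplant participants without abandonment are dropped as not evaluable. In 5.3.9 a failure by the end of the visit window is an event. In both, the visit window is the only time limit on the event.

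**The concern.** Bullet 1 of SAP 5.3.7 has no date limit, and bullet 2 applies only to participants not already caught by bullet 1. The dates compared for the earliest are PD start, transplant, access discontinuation and last data; the failure date is not among them. A programmer following the order would treat a participant transplanted on Day 100 whose fistula fails on Day 200 as a failure at Day 200. An identical participant with no later failure would be censored at Day 100.

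Kaplan-Meier estimation requires that censoring not depend on what happens afterwards. Here, time after transfer enters the risk set only when it ends in failure, which inflates the failure rate. It also mixes loss of a fistula no longer needed for dialysis with the performance of one in use, which the protocol's definition avoids.

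Such failures can be recorded. PD and transplant are not among the discontinuation reasons named in protocol 6.5 (the list is not exhaustive), so follow-up normally continues. Thrombosis seen on DUS, or a maintenance intervention, is itself a failure under 5.3.7.

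**Working it through.** **No stated figure depends on this rule.** The sample size and power calculations concern safety and the intervention rate, so there is nothing in the plan to reproduce.

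**Step 1: direction, ten participants.** Times in days: failures at 30, 90 and 150; censored at 100, 200 and four times at 210; one participant transfers to PD at 60 and has a recorded failure at 120.

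- Protocol rule (censored at 60): day 90 is 0.9 × 7/8 = 78.8%; day 210 is 0.7875 × 5/6 = 65.6%.
- SAP bullets in order (event at 120): day 90 is 0.9 × 8/9 = 80.0%; day 120 is 0.8 × 6/7 = 68.6%; day 210 is 0.6857 × 5/6 = 57.1%.

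The curve is slightly higher between transfer and failure, and lower from the failure onward.

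**Step 2: binary sections.** Assume 100 users, 10 with PD or transplant before the cut-off and 10 other failures. Excluding all 10 transfers gives 80/90 = 88.9%. If 3 of the 10 later fail and are counted, the result is 80/93 = 86.0%.

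**Step 3: size for primary patency.** Inputs from the documents: pre-market primary patency of 72.4% at 6 months (protocol 2.1.2), and attrition of 20%, 40% and 60% at 6, 12 and 24 months (SAP 2.4). Assumed, because the documents are silent: a transfer rate of 0.05 to 0.20 per year, and a post-transfer failure hazard of 0.25 to 2 times the hazard before transfer. The failure hazard is held constant at −ln(0.724)/180 = 0.00179 per day. Kaplan-Meier estimates from 1,000,000 simulated participants per scenario, protocol rule → SAP bullets in order:

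| Transfer per year, hazard multiple | Day 210 | Day 395 | Day 760 | Added events per 150 by Day 760 |
|---|---|---|---|---|
| 0.05, ×0.25 | 68.54 → 68.51% | 49.19 → 49.06% | 25.42 → 24.95% | 0.9 |
| 0.10, ×1 | 68.58 → 68.20% | 49.25 → 48.21% | 25.60 → 23.01% | 4.9 |
| 0.20, ×2 | 68.63 → 66.96% | 49.16 → 45.39% | 25.48 → 18.86% | 13.5 |

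The understatement is 0.03 to 1.7 points at Day 210, 0.1 to 3.8 at Day 395 and 0.5 to 6.6 at Day 760.

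**Step 4: sensitivity.** A second model lets the failure hazard drop to 0.3 per year after 6 months, with the same transfer rates and a post-transfer hazard of 0.3 to 1.0 per year (all assumed). At 0.10 and 0.6 per year there are about 5 added events per 150; patency of about 62.3% becomes 61.0% at 12 months, and 46.1% becomes 42.1% at 24 months. The gap is 1 point or less at 6 months. Across the range it is 0.3 to 3.9 points at 12 months and 1.2 to 10 at 24 months. If post-transfer failures are recorded only to Day 395, the 24-month gap falls from 4.0 to 1.4 points in the middle case and from 9.9 to 4.0 at the top; the 12-month gaps grow slightly.

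**The case against.** **The benign reading.** No sentence in the SAP says that a failure after transfer counts. Bullet 2 does name the PD start and transplant dates, and being without the event can be read as event-free at transfer, which gives the protocol's rule. SAP section 2.7 supports that intent, and the derived data specification (Appendix 2, of which only the title is available) may fix the order. This stands in part: a reader might infer an express SAP rule to count such failures, and the text does not go that far. But bullet 2 ties status to the end of the visit window and not to the transfer date, and the binary sections limit events only by the window. Two programmers could produce different results, one of which contradicts SAP 2.7.3.9.

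**DUS after transplant.** The footnote in protocol 1.3 reads "DUS required at these visits only if participant is not successfully dialyzing with the AVF", and a reader might infer that fistulas unused after transplant must be scanned at 6 and 12 months. Protocol 6.4.1 instead describes participants not yet dialyzing successfully, which fits maturation better than someone who has stopped. No DUS is scheduled after 12 months; the 18- and 24-month contacts are phone calls. Routine detection after transfer is therefore uncertain. Access ligation is an HD continuity intervention (Table 1), so it is not an intervention failure for primary patency.

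**Size.** A reader might take the 10-point gap at 24 months as the expected effect. It needs transfer at 0.20 per year and failures detected at 1.0 per year through Month 24, past the last scheduled scan. The documents support neither rate.

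**Abandonment endpoints.** For 5.3.8 and 5.2.4, protocol 4.4 says that stopping use because of PD or transplant is not abandonment, and the SAP requires that no salvage be possible. Few post-transfer abandonments should be recorded. This stands.

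**Conclusion.** The point holds as a missing date-order condition that conflicts with the plan's own definition. It matters chiefly in SAP 5.3.7 and 5.3.9, where thrombosis and maintenance interventions after transfer can enter as failures, and has little practical effect in 5.3.8 and 5.2.4. Followed in order, the bullets make censoring or exclusion depend on the later outcome and understate patency at time points after the added failures.

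The size cannot be taken from the documents. Under the assumed transfer and post-transfer failure rates it is about 1 to 2 points or less at 6 months, and from under 1 to several points at 12 to 24 months. Three of the endpoints are exploratory and may not be reported (protocol 7.6); cumulative functional patency is a descriptive secondary endpoint. No hypothesis test, power figure or success criterion is affected. It should be corrected before database lock, but it does not threaten the primary conclusions.

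**What to change.** **Kaplan-Meier sections (SAP 5.3.7, 5.3.8).** Add: *A failure counts as an event only if its date is on or before the earliest of PD start, kidney transplant or premature study discontinuation; otherwise the participant is censored at that earliest date regardless of later failures.*

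**Binary sections (SAP 5.2.4, 5.3.9).** Keep the existing visit-window limits and add: *A failure counts only if it also occurs on or before any PD start, kidney transplant or premature discontinuation. A participant whose PD transfer or transplant comes first, before this section's existing window cut-off, is not evaluable for that visit regardless of later failures.* The cut-offs differ (start of the window in 5.2.4, end of the window in 5.3.9) and can stay as they are. The closing bullet of each section should then refer to having no counted failure.

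**Leave access discontinuation out of this cut-off.** Protocol 4.4 treats it as a temporary interruption and does not list it as a censoring event, so a failure after it should still count. Whether the SAP should censor or exclude at access discontinuation at all is a separate discrepancy needing its own decision.

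Align Appendix 2 with this wording. The cost is a few lines of SAP text and one date comparison in the derivation, with no new data collection.
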